12.3.4.2 Clinical Laboratory Assessments

For treatment-emergent laboratory measurements, the raw values and change-from-baseline values of the continuous hematology and chemistry results will be summarized in SI units by treatment group and visit.

The number and percentage of subjects with at least 1 laboratory event outside threshold criteria for the event during the TE period will be summarized overall and by treatment group, including a shift of the event from baseline to post-baseline. The threshold criteria will be provided in the SAP.

A listing of subjects with elevated LFT results during the TE period will be presented based on any of the following: AST $>3 \times$ ULN, ALT $>3 \times$ ULN, GGT $>3 \times$ ULN, ALP $>3 \times$ ULN, or total bilirubin $>2 \times$ ULN. For each subject in the listing, LFT assessments at all time points will be included (scheduled and unscheduled).

Results of the urine/serum pregnancy test will be listed in individual subject data listings only.

In addition, a listing containing individual subject hematology and chemistry values outside the normal reference ranges will be provided. This listing will include data from both scheduled and unscheduled visits.

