9.1 Study 116 Analysis Periods

The Safety analysis period is defined as the **treatment emergent (TE) Period**. The safety analysis period begins at the first dose of study drug in Study 116 Part A and ends 28 days after the last dose of study drug in Study 116 Part A, or at the date of Study 116 Part A participation completion, whichever occurs first.

The safety analyses will be performed on the Safety Set over the Safety Analysis Period, unless otherwise specified.

Safety and tolerability will be assessed by clinical review of all relevant parameters including AEs, Physical Exams, ophthalmologic examinations, clinical laboratory values, vital signs, ECG measurements, and pulse oximetry.

Only descriptive summaries will be presented, and no statistical testing is planned.

Completion of study participation in Study 116 Part A is defined as one of the following:

- For subjects who complete Study 116 Part A and do not roll over to Part B: The Safety Follow-up Visit
- For subjects who complete Study 116 Part A and roll over to Part B or transition to Commercial Drug: The Week 96 Visit
- For subjects who prematurely discontinue study drug treatment but do not withdraw consent in Study 116 Part A: the latest of early treatment termination (ETT) Visit, or Safety Follow-up Visit (if applicable)
- For subjects who withdraw consent in Study 116 Part A: date of withdrawal of consent
- For subjects who are lost to follow-up in Study 116 Part A: the date of last contact

The efficacy analysis period begins at the first dose of study drug in Study 116 Part A and ends at the last study visit at which efficacy data are collected in Study 116 Part A as described in the visit window in the Appendix A. The efficacy analysis will be performed on all subjects in the FAS by parent study for the efficacy analysis period, unless specified otherwise.

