10 STATISTICAL ANALYSIS

10.1 General Considerations

The Schedule of Assessments is provided in the clinical study protocol (CSP) Table 3-1. The precision standards for reporting safety and efficacy variables are provided in an internal Biometrics document that specifies the programming rules including the precision for derived variables.

All individual subject data for subjects who were enrolled in a parent study and who received at least 1 dose of TEZ/IVA in either parent study or in Study 116 will be presented in individual subject data listings.

Continuous variables will be summarized using the following descriptive summary statistics: the number of subjects (n), mean, standard deviation (SD), median, minimum value (min), and maximum value (max).

Categorical variables will be summarized using counts and percentages. Percentages will be presented to 1 decimal place.

Day 1, unless specified otherwise, will be defined as the day of the first dose of TEZ/IVA, in the Study 116 Part A.

Baseline value for safety analysis will be defined as the most recent non-missing measurement (scheduled or unscheduled) collected before the first dose of TEZ/IVA, whether the first dose was taken in the parent study or in Study 116 Part A. For ECGs, the baseline value will be defined as the last non-missing measurement (scheduled or unscheduled) before the first dose of TEZ/IVA or the average of measurements (triplicate) before the first dose of TEZ/IVA, whether the first dose was taken in the parent study or in Study 116 Part A.

Baseline value for efficacy analysis will be defined as the same as baseline of the parent study.

Change (absolute change) from baseline will be calculated as $\frac{\text{Post-baseline value} - \text{Baseline value}}$.

Relative change from baseline will be calculated and expressed in percentage as $\frac{100\% \times (\text{Post-baseline value} - \text{Baseline value})}{\text{Baseline value}}$.

The data from Study 116 will be integrated with data from the parent studies for the purpose of providing robust safety and efficacy analyses.

Unscheduled visits: Unscheduled visit measurements will be included in analysis as follows:

- In scheduled visit windows per specified visit windowing rules.
- In the derivation of baseline measurements.
- In the derivation of maximum/minimum values and maximum/minimum change from baseline values for safety analyses.
- In individual subject data listings as appropriate.

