10.3.2 Clinical Laboratory Values

For laboratory measurements, the raw values and change from treatment baseline values of the continuous hematology, chemistry, vitamin, and lipids results will be summarized in SI units at each scheduled time point in the TE period based on the Safety Set.

The number and percentage of subjects with laboratory measurements meeting threshold criteria during the TE period will be summarized based on the Safety Set for selected laboratory measurements.

The threshold criterion shift from treatment baseline during the TE period will also be summarized for selected LFT laboratory parameters. The threshold criteria are provided in [Appendix G](#).

A listing of subjects with elevated LFT results during the TE period will be presented based on any of the following: AST $>3 \times$ ULN, ALT $>3 \times$ ULN, GGT $>3 \times$ ULN, ALP $>3 \times$ ULN, or total bilirubin $>2 \times$ ULN. For each subject in the listing, LFT assessments at all the time points will be included (scheduled and unscheduled).

In addition, a listing containing individual subject hematology and chemistry values outside the normal reference ranges will be provided. This listing will include data from both scheduled and unscheduled visits.

Only central lab results will be used for the tables. Local lab results will be included in the listings.

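### The SAP keeps the laboratory baseline-shift summary only for selected liver tests, narrower than the protocol, so displayed non-LFT threshold counts mix pre-existing with new abnormality

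*SAP*

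**What the plan says.** Protocol 12.3.4.2 covers subjects with at least one laboratory value outside threshold criteria in the TE period. It says that their number and percentage "will be summarized overall and by treatment group, including a shift of the event from baseline to post-baseline". No parameter is excluded from the shift. The same paragraph hands the criteria to the SAP: "The threshold criteria will be provided in the SAP".

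SAP 10.3.2 splits this into two summaries. The first is a count of subjects "meeting threshold criteria during the TE period will be summarized based on the Safety Set for selected laboratory measurements". The second is the shift, with a narrower scope: "The threshold criterion shift from treatment baseline during the TE period will also be summarized for selected LFT laboratory parameters". The section does not explain the narrowing or mark it as a departure from the protocol.

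For safety, SAP 10.1 takes baseline as the latest non-missing measurement "collected before the first dose of TEZ/IVA, whether the first dose was taken in the parent study or in Study 116 Part A". The counting window is later for many children: "The safety analysis period begins at the first dose of study drug in Study 116 Part A" (SAP 9.1).

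**The concern.** Laboratory values are part of the primary endpoint (Protocol 7.1, SAP 6.1). The study has one treatment arm. SAP 10.3 sets parent-study results beside Study 116 results only for adverse events. For laboratory values, each child's own pre-treatment measurement is therefore the only planned reference.

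A threshold count that ignores that reference answers how many children had an abnormal value while on drug. A safety reader also needs to know how many became abnormal, or became worse, after starting it. For the non-LFT parameters the protocol's shift would supply that number, and the SAP does not plan it.

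**Working it through.** **1. Scope, side by side.** Protocol 12.3.4.2: threshold counts with a shift, no parameter restriction. SAP 10.3.2: threshold counts for selected measurements, shift for selected LFTs. Both statements are complete sentences, so blacked-out text does not explain the difference.

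**2. Rows affected.** Counting the entries of SAP Table 12-3:
- LFT: ALT, AST, ALT or AST, ALP, total bilirubin, direct bilirubin, three transaminase-with-bilirubin combinations, GGT = 10.
- Non-LFT: 12 chemistry + 2 lipid + 5 hematology = 19.

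None of the 19 has a planned shift, and none has a change-from-baseline element. Every band is an absolute value or is set relative to ULN or LLN. By contrast, the ECG criteria (Table 12-4) and the blood pressure and weight criteria (Table 12-5) include change-from-baseline rows, and pulse oximetry has a shift summary (SAP 10.3.5).

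**3. Who is counted.** The count requires only a TE-period value that meets the criterion. A child who met it before any TEZ/IVA and meets it again in the TE period enters the row, and so does a child with a normal baseline. Because baseline precedes any TEZ/IVA, a shift would show change since before the first TEZ/IVA dose, including any that arose during parent-study treatment.

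**4. Other planned outputs.**
- By-visit raw values and changes describe group averages. They give no number of children who crossed a limit.
- The out-of-range listing covers hematology and chemistry. It is a listing without counts, and it does not name lipids.
- TEAE tables pick up laboratory changes that the investigator judged clinically significant (Protocol 13.1.1.2), not every newly met threshold.

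**5. Size.** The plan gives no figure to reproduce. No sample size calculation was made, and no baseline abnormality rates are stated. Two illustrations follow, both using 56 + 65 = 121, the number potentially eligible (SAP 7.2).

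*Direct arithmetic.* Let b be the share meeting the criterion at baseline, p the share of those meeting it again in the TE period, and q the new-onset share in the rest.

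Row count = 121·b·p + 121·(1 − b)·q

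With b = 10%, p = 100%, q = 5% (all assumed):
- already abnormal: 121 × 0.10 × 1.00 = 12.1
- new: 121 × 0.90 × 0.05 = 5.4
- row count: 17.5 (14.5% of 121), of which 12.1 / 17.5 = 69% already abnormal

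Over b = 2–20%, p = 50–100% and q = 2–5%, the share already abnormal runs from 17% to 93%.

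*Simulation with no drug effect.* Normally distributed values, one fixed limit, within-child correlation 0.5 or 0.7, one baseline draw and 9 later draws (Weeks 12 to 96 = 8 visits, plus follow-up), 400,000 children per setting, scaled to 121. A repeat run gave the same results:

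| Assumed baseline prevalence | Meet the row at least once | Of these, already abnormal | Share |
|---|---|---|---|
| 2.5% | 12–16 | about 2 | 12–20% |
| 10% | 36–47 | 10–11 | 21–30% |
| 20% | 59–72 | 22–23 | 30–39% |

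The two illustrations differ because the first fixes new onset at a low rate, while the second lets repeated sampling generate new crossings. The mix therefore depends on unknown inputs, and the planned row gives no way to see it.

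**The case against.** The strongest reply is that this is a matter of display. Safety is descriptive, and no estimate, test or decision rule changes. Protocol 12.3 leaves methodological detail to the SAP, and the shift clause in 12.3.4.2 does not say that it covers every parameter. Protocol 12.3.4 names only hematology and serum chemistry among the laboratory safety endpoints, so the protocol's claim on lipids is weaker. In a study of at most about 121 children, individual baseline status can be traced, and clinically significant worsening reaches the TEAE tables. All of this stands. It does not supply the missing count or explain why the shift was kept for LFTs alone.

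The illustration is also open to criticism. It uses a single limit, whereas Table 12-3 has graded bands, so prevalences of 10–20% could at most resemble the mildest band. Lipids have 5 scheduled post-baseline samples (Weeks 24, 48, 72 and 96, plus follow-up), not 9. A follow-up sample can fall after the TE period has ended. The Safety Set may be smaller than 121. These points stand too, and the counts should be read as illustrative.

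A reader might infer more than the documents support:
- *That every child abnormal before treatment is counted in every non-LFT row.* A child is counted only if a TE-period value also meets that criterion, and only in rows selected for display.
- *That LFT counts are free of the problem.* The plain LFT counts include children abnormal at baseline in the same way. For the selected LFTs, the separate shift summary resolves it.
- *That a shift table would isolate a drug effect.* In the simulation at 10% prevalence, 70–79% of the children counted had a baseline within the limit, although no drug effect was built in. A shift table would show them as worsened.

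**Conclusion.** The mismatch is established from the text. The protocol's shift is not restricted to LFTs, the SAP's is, and the SAP gives no reason. The consequence also follows from the text: wherever a non-LFT threshold row is displayed, pre-existing and new abnormality are combined, and no other planned output gives the number newly abnormal or worsened. This bears on how a component of the primary endpoint can be read, and it changes no inferential result.

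The size is not established. The 10–11 of 36–47 children at 10% prevalence, and the 17% to 93% range from the direct arithmetic, rest on assumed rates. The finding stands without them.

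**What to change.** In SAP 10.3.2, replace the restriction to selected LFTs with a shift summary for every Table 12-3 parameter for which a threshold count is displayed: baseline category against worst TE-period category, on the Safety Set. Beside each threshold count, report the number and percentage of subjects whose worst TE-period category is worse than their baseline category. Treat the high and low directions separately where Table 12-3 has both (for example sodium, potassium, calcium), and show missing baselines as their own category. Add a sentence saying that the shift describes baseline status and does not remove chance crossings from repeated sampling.

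If the sponsor prefers to keep the shift for LFTs only, the SAP should state this as a departure from Protocol 12.3.4.2 and justify it.

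The cost is a change of SAP wording and a few more tables. The baseline and TE-period values are already collected.

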10.3.3 Electrocardiogram

A summary of raw values and change from treatment baseline values will be provided based on the Safety Set at each scheduled time point in the TE period for the following standard 12-lead ECG measurements: RR (msec), HR (beats per minute [bpm]), PR (msec), QRS duration (msec), QT (msec), and QT corrected for HR intervals (QTcF [msec]).

A listing of ECG assessments of subjects with at least 1 abnormal finding will be provided.

The number and percentage of subjects with at least 1 ECG event meeting the threshold criteria during the TE period will be summarized based on the Safety Set in the TE period. The threshold value criteria are provided in [Appendix G](#).

10.3.4 Vital Signs

For vital signs measurements, the raw values and change from treatment baseline values will be summarized based on the Safety Set at each scheduled time point during the TE period for the following measurements: systolic and diastolic blood pressure (mm Hg), body temperature (°C), HR (bpm), and respiration rate (breaths per minute).

The number and percentage of subjects meeting threshold criteria during the TE period will be summarized by vital signs parameters based on the Safety Set. The threshold value criteria are provided in [Appendix G](#).

10.3.5 Pulse Oximetry

For percent of oxygen saturation by pulse oximetry, a summary of raw values and change from treatment baseline values will be provided at each scheduled time point during the TE period based on the Safety Set.

The number and percentage of subjects with shift changes from treatment baseline values (normal/missing and low according to the reference range) to the lowest percent of oxygen saturation during the TE period will be summarized.

The reference range for normal oxygen saturation is specified as >95%, and ≤95% for low oxygen saturation.

10.3.6 Ophthalmologic Examination

Ophthalmologic examination abnormal findings will be presented as a subject data listing.

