7 STUDY ENDPOINTS

7.1 Primary Endpoint

Safety and tolerability of long-term TEZ/IVA treatment based on adverse events (AEs), clinical laboratory values (serum chemistry, hematology, lipids, and vitamins), standard 12-lead ECGs, physical examinations (PEs), vital signs, ophthalmologic examinations, and pulse oximetry

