9.3.3 Rationale for Study Assessments

The safety and efficacy assessments are standard parameters for clinical studies in drug development. The efficacy assessments are widely accepted and generally recognized as reliable, accurate, and relevant to the study of patients with CF.

Ophthalmologic Examinations: A juvenile rat toxicity study performed to support dosing of IVA in subjects <2 years of age demonstrated lens opacities in some animals. Prior studies in rats and dogs of older age did not demonstrate similar findings. Given substantial differences between human and rat lens development, the finding is of unlikely relevance to humans. To confirm this interpretation, periodic ophthalmologic examinations will be performed in this study. The overall data acquired to date do not suggest an association between IVA treatment and cataract development; however, a potential association has not been fully excluded.

LCI Assessment (Subjects From Study 113B LCI Substudy and Study 115 Only): LCI is a measure of ventilation inhomogeneity that is based on tidal breathing techniques which have been evaluated in patients as young as infants.^{4,5} Studies have shown that LCI correlates with

forced expiratory volume in 1 second (FEV₁) in its ability to measure airway disease in patients with impacted spirometry assessment, but can also detect lung disease at an earlier stage than spirometry.^{6,7} Furthermore, data from Study VX10-770-106 in CF subjects with an FEV₁ >90% showed LCI to be a more sensitive outcome measure than FEV₁.

Sweat Chloride: In patients with CF, the underlying CFTR ion transport defect results in elevated sweat electrolyte levels.^{8,9} The sweat chloride test (quantitative pilocarpine iontophoresis) is the most common diagnostic tool for CF. A sweat chloride concentration of ≥60 mmol/L is considered to be diagnostic of CF, whereas <40 mmol/L is considered normal. Based on the mechanisms of action of TEZ and IVA, the sweat chloride test is included in this study as a measure of the effect of TEZ/IVA on CFTR activity.

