12.3.4.6 Other Safety Analysis

Not applicable.

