6 STUDY ENDPOINTS

6.1 Primary Endpoint

Safety and tolerability of long-term TEZ/IVA treatment in Study 116 Part A will be evaluated based on adverse events (AEs), clinical laboratory values (serum chemistry, hematology, lipids, and vitamins), standard 12-lead ECGs, physical examinations (PEs), vital signs, ophthalmologic examinations, and pulse oximetry.

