10.3 Safety Analysis

The primary objective of Study 116 Part A is to evaluate the long-term safety and tolerability of TEZ/IVA. The overall safety profile of study drug will be assessed in terms of the following safety and tolerability endpoints:

- Treatment-emergent adverse events (TEAEs)
- Clinical laboratory values
- Standard 12-lead ECGs
- Vital signs
- Pulse oximetry
- Ophthalmologic examination

Analysis of AEs will be based on events that occur during the TE period of the Part A, for all subjects in the Safety Set. Pooled AE data from Study 113 Part B and Study 115 (only those who received TEZ/IVA) will be displayed side-by-side with AE data from Study 116 Part A. When displayed side-by-side with parent study results, exposure-adjusted rates will be provided.

Other safety analyses will be based on data from the TE period for all subjects in the Safety Set; and will be presented overall. The Safety Set will be used for all listings unless otherwise specified.

Baseline value will be used to calculate change from baseline for continuous safety endpoints.

Only descriptive summaries will be presented, and no statistical testing is planned.

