10.3.1.4 TEAEs of Special Interest

For treatment-emergent elevated transaminase events, respiratory symptoms, and respiratory events (PT lists are provided in

[Appendix H](#)), the following categories will be summarized in terms of frequency counts:

- Subjects with events
- Subjects with events by maximum severity
- Subjects with events leading to treatment discontinuation
- Subjects with events leading to treatment interruption
- Subjects with serious events
- Subjects with related serious events
- Subjects with events leading to death
- Duration of events
- Time-to-onset of first event

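### The planned eye-examination listing cannot give an incidence of new lens opacities among subjects examined; one descriptive table would

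*SAP*

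**What the plan says.** Protocol 7.1 and SAP 6.1 both include eye examinations in the primary endpoint; the SAP's list contains "standard 12-lead ECGs, physical examinations (PEs), vital signs, ophthalmologic examinations, and pulse oximetry". Protocol 9.3.3 explains why. Lens opacities appeared in some animals in a juvenile rat study, and the protocol considers relevance to humans unlikely. It then says: "To confirm this interpretation, periodic ophthalmologic examinations will be performed in this study". On cataract and ivacaftor it adds: "however, a potential association has not been fully excluded".

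Protocol 11.4.7 and Table 3-1 schedule an examination at Day 1 (or up to 28 days later, unless a recent parent-study examination serves), at Week 48, and at Week 96 (±28 days) or Safety Follow-up. Subjects who stop treatment have it at the ETT or Safety Follow-up Visit.

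The planned analysis is the single sentence of SAP 10.3.6: "Ophthalmologic examination abnormal findings will be presented as a subject data listing". SAP Appendix A has no visit window for eye examinations, and Appendix H has no cataract or lens term. Protocol 12.3.4 names the endpoint, but none of its subsections analyses it.

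**The concern.** A listing restricted to abnormal findings shows neither subjects who were examined and found normal nor subjects who were not examined; both are simply absent. It also does not say whether a listed opacity was there before or appeared on treatment. A reader of the study report therefore could not form a rate of new lens opacities or an upper limit for it, although this is the quantity that the examinations were scheduled to inform. The adjacent SAP 10.3.5 plans a shift from baseline for pulse oximetry, another component of the same endpoint, so a summary of this type is already within the plan's style.

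**Working it through.** 1. **The plan's own figure.** The synopsis and Protocol 12.1 give about 56 subjects from Study 113B and 65 from Study 115: 56 + 65 = 121, which agrees with the synopsis. This is potential eligibility, not enrolment and not the number examined. There is no sample-size calculation to reproduce.

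2. **What the listing leaves open.** With zero new opacities among n subjects examined, the exact two-sided 95% upper limit is 1 − 0.025^(1/n). The chance of seeing at least one case at a true risk of 2% is 1 − 0.98^n. The documents do not give n, so the shares of 121 below are assumptions.

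| Share of 121 examined | n | Upper limit, zero cases | Chance of ≥1 case at 2% risk |
|---|---|---|---|
| 100% | 121 | 3.00% | 91.3% |
| 90% | 109 | 3.33% | 88.9% |
| 75% | 91 | 3.97% | 84.1% |
| 50% | 60 | 5.96% | 70.2% |
| 25% | 30 | 11.57% | 45.5% |

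 The limit roughly doubles as the number examined halves. An empty listing fits every row.

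3. **New versus pre-existing.** Suppose, as an assumption, that three subjects are listed. If all three are new among 121 examined, the rate is 3/121 = 2.5% (95% CI 0.5 to 7.1). If all are new among 60, it is 3/60 = 5.0% (1.0 to 13.9). If all three are pre-existing and unchanged among 121, it is 0% (upper limit 3.0%). The planned output does not specify what is needed to choose between these.

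4. **What the adverse-event tables add.** Protocol 13.1.1.1 makes a new or worsened condition an adverse event. SAP 10.3.1 limits TEAEs to new or worsened events in the treatment-emergent period, and SAP 10.3.1.2 tabulates them by preferred term on the Safety Set. So a reported lens event is counted. The denominator, however, is everyone dosed, whether or not examined.

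5. **Timing of the last examination.** Take the last dose as day 0; under Protocol 9.6 the Week 96 Visit is then day 1.
   - SAP 9.1 ends the treatment-emergent period at day 28 or at completion of participation, whichever is first.
   - A Week 96 eye examination may be as late as day 1 + 28 = 29, and a Safety Follow-up Visit as late as day 28 + 7 = 35.
   - For subjects who complete and move to Part B or to commercial drug, completion is the Week 96 Visit, so the period ends on day 1.
   - A lens event dated from an examination after these limits would be a post-treatment event under SAP 10.3.1 and outside the TEAE tables. This is the examination after the longest exposure.

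**The case against.** The strongest reply is that the adverse-event route already provides a count, a percentage and a restriction to new or worsened events. That stands in part. A reader might infer from SAP 10.3.6 that the trial can say nothing about new lens events; the documents do not support that, because cataract reported as an adverse event appears in the ordinary preferred-term tables whether or not it is a special-interest term. The gap is what those tables leave out.

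A reader might also infer that only clinically significant lens findings become adverse events. The documents do not settle this. The clinical-significance test in Protocol 11.4.7 governs notification, and Protocol 13.1.1.2 does not name eye examinations among its examples. It is fair to say only that the protocol gives sites no explicit instruction to record a lens finding as an adverse event.

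It is tempting, too, to read the COVID-19 addendum as showing that eye examinations were missed, because its in-home lists do not mention them. Those lists are non-exhaustive and partly blacked out, and Addendum 3.0 allows make-up visits. Nothing in the documents shows missed examinations.

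Three further points have weight:

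- SAP 10.1 promises listings of all individual data for treated subjects, which could be read to include normal examinations. SAP 10.3.6 reads more narrowly, and even a full listing would leave the count to the reader.
- Physical examinations, also in the primary endpoint, are listing-only under Protocol 12.3.4.5. They are not tied to a specific open question as the eye examinations are.
- Whether eye data exist from before the first TEZ/IVA dose in the parent studies cannot be confirmed here. For subjects treated in the parent study, an examination at its end follows exposure. The fix has to allow for this.

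**Conclusion.** The point holds as a modest reporting gap. The output in SAP 10.3.6 cannot give an incidence of new lens opacities among subjects examined, and the TEAE tables fill the gap only partly: they depend on adverse-event reporting, use the Safety Set as denominator and can miss a late final examination.

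The size is illustrative. With zero new opacities the upper limit is 3.0% for 121 examined and 6.0% for 60. The numbers examined are assumptions, since the documents state only potential eligibility of about 121.

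A reader might infer that a better table would confirm or exclude a cataract association. It would not: a single-arm study of this size can bound the incidence, but cannot by itself exclude an association.

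**What to change.** Keep the listing and add one descriptive table to SAP 10.3.6 giving:

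- the number examined at the reference examination, at Week 48 and at the last examination (Week 96, ETT or Safety Follow-up), including examinations after the treatment-emergent period;
- the number with new or worsened lens opacity or cataract among those examined after the reference examination, with an exact 95% confidence interval.

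Name the reference examination: the parent-study examination before any TEZ/IVA where one exists, otherwise the earliest available. Flag subjects whose reference examination follows TEZ/IVA exposure, including those first dosed in Study 116 whose first examination came after Day 1.

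The interval is descriptive, so the table is consistent with SAP 10.3: "Only descriptive summaries will be presented, and no statistical testing is planned". It adds no examination and changes no clinical procedure. The cost is minor programming. If no examination before TEZ/IVA is available for subjects treated in a parent study, the flag makes that limit visible.
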